## **SCHEDULE OF EVENTS**

Product Name: ADX-629  
Sponsor Name: Aldeyra Therapeutics, Inc.

Protocol: ADX-629-PS-001  
Protocol Date: June 9, 2021, v3.0

## ABBREVIATIONS

ACE	Angiotensin-converting Enzyme
AE	Adverse Event
ALT	Alanine Aminotransferase
AST	Aspartate Aminotransferase
AUC	Area Under the Curve
β-hCG	Beta-Human Chorionic Gonadotropin
BID	Bis In Die (Twice daily)
BSA	Body Surface Area
BUN	Blood Urea Nitrogen
CFR	Code of Federal Regulations
CLIA	Clinical Laboratory Improvement Amendments
C max	Maximum Concentration
CTCAE	Common Terminology Criteria for Adverse Events
ECG	Electrocardiogram
eCRF	Electronic Case Report Form
EDC	Electronic Data Capture
eGFR	Estimated Glomerular Filtration Rate
ELISA	Enzyme-Linked Immunosorbent Assay
EOS	End of Study
EOT	End of Treatment
FDA	Food and Drug Administration
FSH	Follicular Stimulating Hormone
GGT	Gamma-Glutamyltransferase
HDL	High-Density Lipoprotein
HIV	Human Immunodeficiency Virus
IB	Investigator's Brochure
I/E	Inclusion/Exclusion
IGA	Investigator's Global Assessment
IND	Investigational New Drug
IRB	Institutional Review Board
IU	International Units
IUD	Intrauterine Device
L	Liter
LDH	Lactate Dehydrogenase
LDL	Low-Density Lipoprotein
MAD	Multiple Ascending Dose
MCH	Mean Corpuscular Hemoglobin
MCHC	Mean Corpuscular Hemoglobin Concentration
MCV	Mean Corpuscular Volume
MDA	Malondialdehyde
miU	Milli International Units

mL	Milliliter
NOAEL	No-Observed-Adverse-Effect Level
OTC	Over-the-Counter
PASI	Psoriasis Area Severity Index
PGIC	Patient Global Impression of Change
PK	Pharmacokinetic
PO	Per Os (Orally)
PT	Preferred Term
RASP	Reactive Aldehyde Species
RBC	Red Blood Cells
RDW	Red Blood Cell Distribution Width
RNA	Ribonucleic Acid
SAD	Single Ascending Dose
SAE	Serious Adverse Event
SGOT	Serum Glutamic Oxaloacetic Transaminase
SGPT	Serum Glutamic Pyruvic Transaminase
SOC	System Organ Class
t 1/2	Half Life
TI	Therapeutics, Incorporated
ULN	Upper Limit of Normal
UPT	Urine Pregnancy Test
WBC	White Blood Cells
WHO	World Health Organization
WOCBP	Women of Childbearing Potential

## 1. BACKGROUND

Reactive aldehyde species (RASP) such as 4-hydroxynonenal and malondialdehyde (MDA) are toxic mediators of the mammalian immune system and are implicated in numerous disease states. The Sponsor has developed ADX-629, a proprietary new chemical entity for the treatment of immune-mediated diseases, including psoriasis, asthma, inflammatory bowel disease, alcoholic and non-alcoholic hepatitis, acute respiratory distress syndrome, and other diseases that are thought to be caused or exacerbated by elevated concentrations of RASP.

MDA is elevated in the plasma of patients with psoriasis [1], reaching levels of approximately 4 $\mu$ M, roughly twice that of healthy subjects. A recent review [2] highlights the correlation of MDA levels with psoriasis area severity index (PASI), as well as increased levels of MDA in patients with genetic polymorphisms that increase the risk of psoriasis.

[REDACTED]

[REDACTED]

[REDACTED]

In addition to nonclinical safety studies, Phase 1 safety testing has been conducted in 85 healthy human volunteers in a single ascending dose (SAD) and a multiple ascending dose (MAD) clinical trial. In the SAD portion of the clinical trial, 41 subjects received drug and 13 received placebo across all cohorts. In the MAD portion of the clinical trial, 23 subjects received drug and 8 received placebo across all cohorts for 10 days. Overall, ADX-629 was found to be safe and tolerable at the doses explored, including the maximum single dose of 1200 mg and the maximum multiple dose of 600 mg BID for 10 days. The adverse event profile of ADX-629 was favorable compared to placebo. A total of 6 (9.4%) subjects receiving ADX-629 had treatment emergent adverse events compared to 4 (19.1%) subjects who received placebo. None of the subjects had an interruption or discontinuation of the trial drug.

Although PK variability was observed, a linear correlation was evident in  $C_{max}$  and AUC as dose increased. The half-life ( $t_{1/2}$ ) was consistent across cohorts and days, with mean values in multiple day exposures ranging between 3.49 to 6.83 hours, supportive of BID administration. Little to no accumulation of the drug was seen across all cohorts. At the top dose (600 mg BID), a  $C_{max}$  of 1920 ng/mL (approximately 9.5  $\mu$ M) was consistent with an adequate molar ratio to achieve stoichiometric efficacy against elevated RASP in psoriasis, as described above. Importantly, MDA levels in drug-treated subjects were statistically lower than those of placebo-treated subjects, and inflammation following ingestion of a fatty meal at Day 10, as assessed by lipid profiling, was statistically lower in the drug group relative to the placebo group.

In summary, mechanistic, preclinical, and clinical data suggest that administration of the RASP inhibitor ADX-629 to subjects with plaque psoriasis may sufficiently mitigate the inflammatory response to modify levels of inflammatory mediators and reduce clinical severity.

## 2. RATIONALE

The starting dose for ADX-629 is based on the doses studied in nonclinical studies and the Phase 1 healthy volunteer clinical trial. In nonclinical studies, the human equivalent of 250 mg BID PO for 91 days resulted in acceptable safety profiles. In the Phase 1 clinical trial, the highest multiple dose tested of 600 mg BID for a period of 10 days was found to be safe and tolerable with no adverse events of clinical concern noted. Based on the Phase 1 clinical trial PK results, the anticipated  $C_{max}$  at 250 mg BID is approximately 3.3  $\mu$ M, which, based on preclinical results in models of severe inflammation and published levels of MDA in patients with psoriasis, is in the range of active concentrations.

### **3. OBJECTIVE**

The objective of ADX-629-PS-001 is to evaluate the safety, tolerability, and efficacy of ADX-629 in subjects with plaque psoriasis.

### **4. TRIAL DESIGN**

ADX-629-PS-001 is a multi-center, open-label trial of ADX-629 in adult subjects with stable plaque psoriasis. Approximately 10 subjects with stable moderate to severe plaque psoriasis (Investigator's Global Assessment [IGA] score  $\geq 3$ , PASI score of  $\geq 12$ , and body surface area [BSA]  $\geq 8\%$ ) who fulfill the inclusion/exclusion (I/E) criteria will be enrolled at approximately 2 trial sites in the United States. All subjects will be assigned to the following treatment group in an open-label manner.

- ADX-629, 250 mg BID for 12 weeks

All subjects will administer the test article orally (PO) BID.

Subjects will have 7 trial visits: 5 in-person visits and 2 phone calls. Activity will be assessed via PASI, Skin Biomarker Analysis, Blood Biomarker Analysis (RASP enzyme-linked immunosorbent assays [ELISAs] and cytokine levels), IGA, and Patient Global Impression of Change (PGIC). Safety will be assessed by vital signs, physical examinations, clinical laboratory tests, electrocardiogram (ECG), and adverse events (AEs). Metabolite profiling will be assessed by urine and plasma drug metabolite analysis.

### **5. TRIAL POPULATION**

#### **5.1 Subject Eligibility**

To be included in the trial, subjects must meet the following inclusion and none of the exclusion criteria.

##### ***5.1.1 Inclusion Criteria***

1. Subject is a male or non-pregnant female 18 years of age or older.
2. Subject has provided written informed consent.

3. Females must be post-menopausal, surgically sterile, or use a highly effective method of birth control during the trial and for 30 days after the last administration of test article. Women of childbearing potential (WOCBP) must have a negative urine pregnancy test (UPT) at Visit 1/Screening and Visit 2/Baseline.
4. Male subjects who are not surgically sterile (e.g., vasectomy performed at least 6 months prior to trial entry) and are sexually active with a female partner who is of childbearing potential must agree to use an effective form of birth control for the duration of the trial and for 90 days after completion of treatment.
5. If male, subject agrees to refrain from sperm donation during the trial and for 90 days after completion of treatment.
6. Subject has a clinical diagnosis of moderate to severe stable plaque psoriasis for at least 6 months with a PASI score  $\geq 12$ , an IGA of  $\geq 3$ , and an affected BSA of  $\geq 8\%$  at Visit 2/Baseline.

---

 Defined as spontaneous amenorrhea for at least 1 year in women 50 years of age and older.

 Hysterectomy, bilateral tubal ligation, salpingectomy, or bilateral oophorectomy at least 26 weeks prior to Visit 2/Baseline.

 Highly effective forms of birth control for FEMALE subjects include 1) intrauterine device (IUD; copper or hormonal); 2) implantable hormonal contraception; 3) monogamous relationship with a partner who is sterile (e.g., vasectomy [performed at least 6 months prior to study entry]); 4) total abstinence; or 5) using one of each of the following a) hormonal contraceptives [other than IUD or implantable, e.g., oral, transdermal, injectable, or vaginal ring] and b) double barrier methods [i.e., male or female condom, diaphragm with spermicidal foam/gel/film/cream/vaginal suppository, cervical cap with spermicides, or contraceptive sponge]. Also see next footnote for the required duration of birth control prior to test article application. Subjects who become sexually active or begin to have relations with a partner who is not sterile during the trial must agree to use a highly effective form of birth control for the duration of the trial.

 WOCBP taking hormonal therapy must be on treatment prior to trial entry, continued per label, and must not change their dosing regimen during the trial; highly effective birth control forms must be for (1) oral: at least 1 complete cycle (e.g., 4 to 8 weeks); (2) transdermal, injectable (e.g., Depo-Provera), implantable, vaginal ring (e.g., NuvaRing), IUD: at least 1 week; or (3) total abstinence: at least 1 complete cycle (e.g., 4 to 8 weeks) prior to initiation of test article.

 UPT must have a minimum sensitivity of 25 mIU  $\beta$ -hCG/mL.

 WOCBP include any female who has experienced menarche or is 10 years of age or older and who has not undergone successful surgical sterilization (hysterectomy, bilateral tubal ligation, salpingectomy, or bilateral oophorectomy at least 26 weeks prior to Visit 2/Baseline) or is not postmenopausal (defined as amenorrhea for at least 1 year in women 50 years of age and older).

 Effective forms of birth control for MALE subjects include: 1) male condom with spermicide; or 2) use by the female sexual partner of a) hormonal contraceptives [e.g., oral stabilized for at least 1 complete cycle (e.g., 4 to 8 weeks); transdermal, injectable (e.g., Depo-Provera), implantable, or vaginal ring (e.g., NuvaRing) stabilized for at least 1 week prior to trial entry or initiation of sexual relations], b) IUD (with or without hormones) for at least 1 week prior to test article dosing, or c) a barrier method [e.g., female condom, contraceptive sponge, diaphragm, or cervical cap] with spermicide. Abstinence is also an acceptable method of birth control for subjects who are not sexually active. Subjects who become sexually active or begin to have relations with a female partner who is of childbearing potential during the trial must agree to use an effective form of birth control for the duration of the trial and for 90 days after completion of treatment.

[figure not shown]
7. Subject has normal renal function at Visit 1/Screening, defined as an estimated glomerular filtration rate (eGFR) of  $\geq 90$  mL/min/1.73 m^2 calculated by Chronic Kidney Disease Epidemiology Collaboration equation in the absence of hematuria, proteinuria, or glycosuria on urine analysis by dipstick. Urine albumin must be  $< 30$  mg/gram creatinine by laboratory measurement.
8. Subject agrees to avoid smoking tobacco and all other nicotine containing products (e.g., vaping, gum, patches, chewing, or dip products, etc.) for the duration of the trial.
9. [REDACTED]
10. Subject agrees to avoid taking the following concomitant medications: strong CYP1A2, 2B6, and 3A4 inhibitors for the duration of the trial.
11. Subject is willing and able to administer the test article(s) as directed, comply with trial instructions, and commit to all follow-up visits for the duration of the trial.
12. Subject, in the investigator's opinion, is in good general health and free of any disease state or physical condition that might impair evaluation of plaque psoriasis or exposes the subject to an unacceptable risk by trial participation.

#### **5.1.2 Exclusion Criteria**

1. Subject is pregnant, lactating, or is planning to become pregnant during the trial.
2. Subject has guttate, pustular, erythrodermic, drug-induced, or other non-plaque forms of psoriasis.
3. Subject has a physical condition which, in the investigator's opinion, might impair evaluation of plaque psoriasis or which exposes the subject to an unacceptable risk by trial participation.
4. Subject has acute or chronic renal disease or medical history of renal disease that, in the opinion of the investigator, could compromise the subject's safety.
5. Subject has a history or presence of gastrointestinal, hepatic, or renal disease, or any other condition known to interfere with absorption, distribution, metabolism, or excretion of drugs.
6. Subject has an active infection at Visit 2/Baseline that precludes the subject's participation in the opinion of the investigator.
7. Subject has a history of cancer, with the exception of cancers considered nonmelanoma skin cancers (e.g., squamous cell carcinoma, basal cell carcinoma) in the opinion of the investigator.

---

 If eGFR and/or urine albumin lab assessments are close to, but outside of the limits specified and the lab results are deemed not to be clinically significant by the Investigator, the Investigator may request a review by the Medical Monitor of the lab finding(s) in writing to determine the subject's eligibility. The Medical Monitor will review the subject's medical history and concomitant medications in conjunction with the lab results. If the Medical Monitor concurs with the Investigator's assessment of the lab results and assuming that the subject is otherwise qualified to participate, the subject may be enrolled in the study upon receipt of a written approval of the Medical Monitor prior to enrollment.

8. Subject has clinically significant laboratory results at Visit 1/Screening that precludes the subject's participation in the opinion of the investigator.
9. Subject has used any phototherapy (including laser), photo-chemotherapy, or other forms of photo based therapy for the treatment of their psoriasis within 90 days prior to Visit 2/Baseline.
10. Subject has used systemic tofacitinib, apremilast, methotrexate, retinoids, systemic corticosteroids (including intralesional, intra-articular, and intramuscular corticosteroids), cyclosporine, or analogous products within 90 days prior to Visit 2/Baseline.
11. Subject has used any systemic immunosuppressant biologic therapy (i.e., FDA-approved or experimental therapy) within 5 half-lives of the biologic prior to Visit 2/Baseline. Published or documented half-life of the product provided by the commercial supplier or Sponsor should be used to establish this value.
12. Subject is taking concomitant medication or therapy that affects renal or hepatic function, in the opinion of the investigator
13. Subject has had prolonged exposure to natural or artificial sources of ultraviolet radiation within 30 days prior to Visit 2/Baseline or is intending to have such exposure during the trial which, in the opinion of the investigator, is thought to modify the subject's disease.
14. Subject has used topical body psoriasis therapy (including coal tar, anthralin, steroids, retinoids, and vitamin D analogs) within 14 days prior to Visit 2/Baseline.
15. Subject has used emollients/moisturizers on areas to be treated within 4 hours prior to clinical evaluation at Visit 2/Baseline.
16. Subject is currently using lithium or Plaquenil (hydroxychloroquine).
17. A large rectangular area of the page is completely blacked out, indicating redacted information.
18. Subject is currently enrolled in an investigational drug, biologic, or device trial.
19. Subject has used an investigational drug, investigational biologic, or investigational device treatment within 30 days prior to Visit 2/Baseline.
20. Subject has a history of sensitivity to any of the ingredients in the test article (see Section 6.1).
21. Subject is known to be noncompliant or is unlikely to comply with the requirements of the trial protocol (e.g., due to alcoholism, drug dependency, mental incapacity) in the opinion of the investigator.

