### **8.2 Allowed Medications or Therapies**

Vitamins and mineral supplements are permitted at dosages considered by the investigator as reasonable for maintaining good health and will not be recorded in the eCRFs. Therapies (medication and non-medication therapies) not restricted by the protocol may be used during the trial for the treatment or prevention of disease or to maintain good health. Non-prohibited chronic therapies being used at Visit 1/Screening may be continued, but must be recorded.

Approved bland moisturizers/emollients (as detailed on a list of such products to be provided by the sponsor or their designee) may be used once daily, but must be recorded as a concurrent procedure. Use of bland moisturizers/emollients more than once daily must be approved by written permission of the Medical Monitor.

OTC shampoo products containing selenium sulfide, zinc pyrithione, and/or salicylic acid as active ingredient(s) may be used to help control inflammatory scalp conditions including scalp psoriasis, but must be recorded as a concomitant medication.

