### 9.3 Visit 3 (Day 15 ± 2): Phone Call

*During this phone call, the investigator or designee will:*

- Query the subject for any changes in health status since the previous visit, including concomitant medications and concurrent procedures/therapies, and document the findings.
- Remind the subject to continue to take 1 tablet twice daily until the next clinic visit.
- Discuss any AEs to determine if the subject should return to the study site for an unscheduled visit.

 WOCBP include any female who has experienced menarche or is 10 years of age or older and who has not undergone successful surgical sterilization (hysterectomy, bilateral tubal ligation, salpingectomy, or bilateral oophorectomy at least 26 weeks prior to Visit 2/Baseline) or is not postmenopausal (defined as amenorrhea for at least 1 year in women 50 years of age and older). Post-menopausal status must also be confirmed with FSH test results from Visit 1/Screening.

- Confirm the next visit.

#### 9.4 Visit 4 (Day 29 ± 3): Week 4

**One day prior to the visit, the site staff will contact the subject to remind them that if the subject chooses to take the morning dose of test article at home on the day of their clinic visit, the subject should: 1) take the morning dose of test article approximately 2 hours prior to the study visit AND 2) note the time of dosing on the Subject Instruction Sheet. Subject will also be informed that if the subject chooses to take the morning dose of test article in the clinic, the subject will need to remain in the clinic for 2 hours after dosing.**

*At this visit, the investigator or designee will:*

- Query the subject for any changes in health status since the previous visit, including concomitant medications and concurrent procedures/therapies, and document the findings.
- Measure vital signs (see Section 10.7.1).
- Have the subject perform the subject evaluation (PGIC). See Section 10.6.
- Perform clinical evaluations (IGA first, then BSA and PASI). See Section 10.3, Section 10.5, and Section 10.4, respectively.
- Perform a targeted physical exam (see Section 10.7.2). Record any new or worsening clinically significant abnormalities as AEs.
- Perform ECG (see Section 10.7.3).
- From the same area collected at baseline, collect non-invasive skin sample from lesional skin for subjects (see Section 12.2).
- Review compliance.
- Document Test Article Accountability; all test articles will be collected and tablets will be counted.

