### 10.3 Investigator's Global Assessment

The IGA score is a static evaluation of the overall severity or “average” degree of severity of a subject’s disease, taking into account all of the subject’s psoriatic lesions (excluding those on the face, scalp, groin, axillae, and other intertriginous areas) by the investigator or designee as the subject appears on the day of the evaluation. The evaluation takes into consideration the 3 individual characteristics of psoriasis (plaque elevation, scaling, and erythema) with the IGA score at each visit representing the average degree of plaque elevation, scaling, and erythema that is present amongst all of the lesions.

**The investigator should NOT refer to any other assessments to assist with this evaluation.** This evaluation is NOT a comparison with the IGA at any other visit or a mathematical calculation based on the clinical signs of psoriasis scores. At every trial visit, the investigator or designee will evaluate all active psoriasis plaques in the subject’s entire body) and report the one whole integer score that describes the average IGA using the following scale:

CLEAR (0)	
Plaque elevation	No evidence of plaque elevation above normal skin level.
Scaling	No evidence of scaling.
Erythema	No erythema (hyperpigmentation may be present).

ALMOST CLEAR (1)	
Plaque elevation	No more than a very slight elevation above normal skin level, easier felt than seen.
Scaling	No more than limited amount of very fine scales partially covers some of the plaques.
Erythema	No more than faint red coloration.

MILD (2)	
Plaque Elevation	No more than a slight but definite elevation above normal skin level, typically with edges that are indistinct or sloped, on some of the plaques.
Scaling	No more than mainly fine scales; some plaques are partially covered.
Erythema	No more than light red coloration.

MODERATE (3)	
Plaque Elevation	No more than a moderate elevation with rounded or sloped edges on most of the plaques.
Scaling	No more than somewhat coarser scales predominate; most plaques are partially covered.
Erythema	No more than moderate red coloration.

SEVERE (4)	
Plaque elevation	Marked elevation with hard sharp edges on virtually all of the plaques.
Scaling	Coarse, thick tenacious scales predominate; virtually all or all plaques are covered; rough surface.
Erythema	Dusky to deep red coloration.

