#### 10.4 Psoriasis Area and Severity Index

The severity of plaque psoriasis by body region (head, upper limbs, trunk, and lower limbs) and the percentage area affected by body region will be assessed. For each body region, erythema, induration/thickness, and scaling will be graded using a 5-point scale (0=clear, 1=slight (mild), 2=moderate, 3=severe, 4=very severe) and the percent involvement of each body region will be assigned a numeric score (from the BSA assessment described below): 0% (0), 1% – 9% (1), 10% – 29% (2), 30% – 49% (3), 50% – 69% (4), 70% – 89% (5) or 90% – 100% (6). The sign scores for each body region will be summed and multiplied by

the Area Score, and then multiplied by the amount of body surface area assigned to that body region (0.1 for head, 0.2 for upper limbs, 0.3 for trunk, and 0.4 for lower limbs). The sum of PASI scores by body region will give the total PASI score, which may range from zero (0) to a maximum of 72. See Appendix 3.

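### The readable protocol sets an emollient-free interval before grading at Baseline only, so PASI and IGA change scores can drift toward improvement without any drug effect

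*Protocol*

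**What the plan says.** **Baseline.** Protocol 5.1.2, item 15 (repeated in the Synopsis) excludes a subject if "Subject has used emollients/moisturizers on areas to be treated within 4 hours prior to clinical evaluation at Visit 2/Baseline". No other visit is named.

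**During the trial.** Protocol 8.2 says that approved bland products "may be used once daily, but must be recorded as a concurrent procedure". It adds: "Use of bland moisturizers/emollients more than once daily must be approved by written permission of the Medical Monitor". Neither sentence sets a time of day or an interval before a visit, and neither asks for the time of application.

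**Follow-up grading.** The step for Visit 4 in Protocol 9.4 reads "Perform clinical evaluations (IGA first, then BSA and PASI"; Visits 5 and 6 (9.5 and 9.6) repeat it. No emollient check appears among the steps. The call made the day before each of these visits deals with dose timing only. Sections 10.3 to 10.5, which tell the grader how to score, set no emollient condition.

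**What is scored.** For PASI (Protocol 10.4), "erythema, induration/thickness, and scaling will be graded using a 5-point scale" in each body region. For the IGA (10.3), "The evaluation takes into consideration the 3 individual characteristics of psoriasis (plaque elevation, scaling, and erythema" among them.

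**How it is used.** SAP 8.7.1 names change from Baseline in PASI as the primary clinical efficacy endpoint and change in IGA as the key secondary. SAP section 5 takes Baseline from Visit 2. SAP 8.8.9 lists concurrent procedures, and no analysis uses emollient records.

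**The concern.** By writing exclusion 15, the sponsor accepted that recent emollient use can affect the clinical evaluation. The same reasoning applies to the later gradings, because a change score has two ends. In the readable text only the Baseline end is controlled.

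The imbalance has a direction. If a recently applied emollient makes scale less visible, that can happen at Weeks 4, 8 and 12 but not at Baseline, and the change score moves toward improvement. The documents do not describe the effect of emollient on grading, so this direction is an inference from the purpose of exclusion 15.

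In a randomised comparison the shift would be expected in both arms and would largely cancel. Here all subjects receive ADX-629 open-label, so any shift is read as drug effect. The planned analysis cannot remove it: the records can show who used emollients, but not how long before grading.

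**Working it through.** **Inputs from the documents**
- Region weights 0.1, 0.2, 0.3 and 0.4, which sum to 1.0; three signs scored 0 to 4; area score 0 to 6 (Protocol 10.4).
- Entry threshold: PASI of at least 12 at Baseline (Protocol 5.1.1, item 6).
- About 10 subjects, one arm (Protocol section 4).

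**Assumptions, with no source in the documents**
- Signs and area scores are equal across regions.
- In an affected subject, scaling is graded one point lower in every region; erythema, induration and area do not change.

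**Formula.** PASI = sum over regions of weight × area score × (erythema + induration + scaling). With equal regions this becomes area score × sign sum × 1.0.

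**Check against the protocol's own figure.** Section 10.4 gives a total "which may range from zero (0) to a maximum of 72". All signs 4 and all area scores 6 give 12 × 6 × 1.0 = 72, which agrees.

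**One-grade fall in scaling, one subject**

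| Signs (E/I/S) | Area score | PASI before | PASI after | Fall |
|---|---|---|---|---|
| 2/2/2 | 2 | 6 × 2 = 12 | 5 × 2 = 10 | 2.0 (2/12 = 16.7%) |
| 3/3/3 | 2 | 9 × 2 = 18 | 8 × 2 = 16 | 2.0 (2/18 = 11.1%) |
| 4/4/4 | 2 | 12 × 2 = 24 | 11 × 2 = 22 | 2.0 (2/24 = 8.3%) |
| 2/2/2 | 3 | 6 × 3 = 18 | 5 × 3 = 15 | 3.0 (3/18 = 16.7%) |

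The absolute fall equals the area score, and the percentage fall is 1 / sign sum.

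**Shift in mean PASI change.** At area score 2, the shift is -2.0 × share of subjects affected:
- 0%: 0
- 20% (2 of 10): -0.4
- 50% (5 of 10): -1.0
- 100%: -2.0

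**Responder endpoints.** With equal signs, removing scaling entirely lowers PASI by one third (33.3%), which is short of 50%. Scaling alone reaches 50% only where it makes up at least half of the sign sum, for example 2/2/4 falling to 2/2/0 (8 to 4). A one-grade fall does reduce what else is needed for PASI-50: from 3.0 to 2.0 points of sign sum at 2/2/2, or from 4.5 to 3.5 at 3/3/3.

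**IGA.** Section 10.3 says the score is not calculated from the sign scores, so no corresponding shift can be computed.

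**With matched conditions.** If the same interval preceded every grading, the part of the scaling score due to a different interval would be about equal at both ends and would drop out of the change. No sample size or power figure changes, because none was calculated (Protocol 17.1).

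**The case against.** The strongest objection is that the point rests on an absence, and some places where a rule could sit cannot be read. The list in Protocol 8.1 is redacted, and the Schedule of Events and the Subject Instruction Sheet (Appendix 2) are not shown. The sponsor's list of approved emollients might also carry conditions of use. This stands: the finding concerns the readable text, and the fix must allow for a rule elsewhere.

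The trial is also described as primarily one of safety and tolerability, with about 10 subjects and descriptive summaries. No test depends on PASI, and a single open-label arm cannot separate drug effect from natural course or grader expectation in any case. That limits the importance of the point but does not remove it. Efficacy is a stated objective, and this source of drift, unlike those, can be removed at almost no cost.

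Three stronger readings might be inferred, and the documents support none of them.
- *Section 8.2 contradicts any matching rule.* It is silent on timing. Once-daily use is compatible with a bar shortly before visits, since a subject could apply the product afterwards.
- *Emollients are allowed only after Baseline.* Section 8.2 is not limited to that period, and exclusion 15 covers only the last 4 hours before grading. The asymmetry lies in time since last application, not in whether emollients are used.
- *Emollients could by themselves produce responders, or a fall of a third in PASI.* At signs 2/2/2, a 33.3% fall requires all scale to disappear in all four regions, and even that misses PASI-50.

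**Conclusion.** The concern holds for the readable text: a grading condition thought necessary at Baseline is not carried to Visits 4, 5 and 6, and this can bias mean change in PASI and IGA toward improvement. The documents give no emollient effect, so the size is unknown. Under the stated assumptions the shift in mean PASI change runs from 0 to -2.0 points at area score 2, depending on how many subjects are graded soon after application and lose one scaling grade. PASI-50 and PASI-75 are unlikely to be met through scaling alone, although a subject already close to a threshold could be carried over it. The conclusion also depends on there being no matching rule in the redacted or missing pages, which the sponsor can check directly.

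**What to change.** First check Protocol 8.1, the Schedule of Events and Appendix 2. If a matching rule is there, cite it in 8.2 and in 9.4 to 9.6; nothing more is needed.

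If not, reconcile exclusion 15 with 8.2 and 9.4 to 9.6:
- state that the protocol's own 4-hour Baseline condition also applies before IGA, BSA and PASI grading at Visits 4, 5 and 6;
- mention it in the call already made the day before each of those visits;
- record the time of last emollient application at each graded visit, including Baseline, so that departures can be seen in the listings.

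The cost is a sentence or so in each affected section, one line in an existing call, one recorded time per visit, and minor inconvenience to subjects. Treatment, visit schedule and sample size are unaffected.
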